**Protocol: The Impact of Physiologic Cataract Surgery on Patient Comfort and Medication Usage**

**IIT 98621123 - [name]**

**DATE: 10-03-2025**

## **Protocol: The Impact of Physiologic Cataract Surgery on Patient Comfort and Medication Usage**

**IIT 98621123 - [name]**

**NEED** The advanced fluidics of Unity VCS/CS allow a more physiologic cataract surgery environment. Limited research exists comparing the surgical experience for patients between Unity VCS/CS and Centurion with regards to patient comfort and pain.

**STUDY OBJECTIVE** To investigate the impact of Unity VCS/CS with Intelligent Fluidics at a low IOP setting and Centurion with Active Sentry at a traditionally high IOP setting on the intraoperative experience for the patient and surgeon

**STUDY HYPOTHESIS** Unity VCS/CS with Intelligent Fluidics during cataract surgery will result in significantly less discomfort/pain as assessed by the decreased need for rescue medication and lower VAS scores.

**SUPPORTS CLINICAL MESSAGE** Unity VCS/CS allows for phacoemulsification at a more physiologic IOP with lower patient reported discomfort/pain and less pharmacologic use as compared to Centurion with Active Sentry at a traditionally higher intraoperative IOP

### **STUDY DESIGN**

Cohort	Bilateral visually significant cataract surgery	Endpoints	
Primary endpoint: % of pts in each group requiring rescue medication for breakthrough discomfort/pain
 
Secondary endpoints:
 

• Discomfort/pain score at phaco, I/A, visco removal

• Surgeon Experience: Assessment on cooperation & experience

• Cost-analysis on intraoperative medications utilized in low and high IOP groups

• Breakthrough pain and discomfort/pain score on subjects with axial length of >24.5mm

• Post op day 1 patient survey on experience (Iowa Satisfaction with Anesthesia Scale (ISAS)

• Post op day 1 survey on patient preference - What eye was more comfortable? (R/L)

• What surgical experience did you enjoy more? (R/L)

• x% of eyes would undergo the same procedure again

• x% of eyes would recommend the procedure to family and friends

• Time Interval between Surgery Completion and Discharge from Facility

• Physiologic responses by masked anesthesiologist: BP, pulse rate

Alcon Product	Unity VCS/CS with Intelligent Fluidics	Design	Prospective, single-surgeon, eyes undergoing phacoemulsification will be randomized to low (IOP 25mmHg) or high (IOP 65mmHg) IOP, contralateral eye will receive other treatment
Comparator	Centurion with Active Sentry (AS)	Time of follow-up	POD1

SAMPLE SIZE 85 subjects (170 eyes)
 
STUDY DURATION (Contract execution to CSR) 13 Months
			

**Introduction:**

The study will pertain to investigating the impact of high vs low IOP on the intraoperative experience and comfort for the patient and surgeon. Our hypothesis is that operating at a more physiological IOP using Unity VCS/CS and Centurion with Active Sentry at a higher, or more traditional IOP will result in significantly less discomfort/pain as assessed by the decreased need for rescue medication and lower VAS scores.

**Background:**

Although topical anesthesia provides for high patient comfort during cataract surgery, certain parts of the cataract procedure are associated with more patient discomfort. To further increase patient comfort while undergoing cataract surgery under topical anesthesia, it was proposed to add intracameral lidocaine. Injection of intraocular lidocaine increases patient cooperation and decreases the degree to which patients are bothered by tissue manipulation, two outcomes that justify its use.

It is plausible that the use of intracameral lidocaine became 'routine care' in an era where surgeons strived for more efficient cataract surgery through altering fluidics by increasing vacuum level, flow rate, and infusion pressure. The desire for increased efficiency also led to the addition of a variety of other pharmacological agents, such as sympathomimetic agents, other analgesics, NSAIDs, opioids, etc.

Despite technological and procedural advances in ophthalmic surgery, the prescription rate for opioids after ophthalmic procedures, including cataract surgery, has been paradoxically increasing

In Scarfone et al., the patient's subjective perception of pain was significantly lower for the low intraoperative pressure group (IOP 30 mmHg) as compared to high IOP group (80 mmHg) according to the Wong Baker faces scale

In Rauen et al., lower intraoperative pressures at the time of cataract surgery were associated with less pain by real-time VAS scoring and less medication usage.

The PI has completed thousands of cataract surgeries with physiologic (low) IOP (intraocular pressure) and standard (high) IOP (intraocular pressure). A previous study completed at our facility showed equivalent visual outcomes between the two conditions at day 1, 7, 30, and 90. Additionally, case time did not differ between the two conditions. A preliminary study completed by the PI suggested physiologic (low) IOP surgery was more comfortable by Visual Analogue Scale (VAS). Furthermore, in this same pilot study, physiologic (low) IOP surgery led to less narcotic and less anxiolytic medication use. While we recognize that high IOP surgery is standard of care, more physiologic (low) IOP surgery again has been proven safe and may be more comfortable.

**Objective/ Unmet Medical Need:**

To investigate the impact of Unity VCS/CS with Intelligent Fluidics at a low IOP setting and Centurion with Active Sentry at a traditionally high IOP setting on the intraoperative experience for the patient and surgeon. Limited research on phacoemulsification at near physiological IOP and its impact on patient discomfort/pain using the Unity VCS/CS system.

**Design:**

Prospective, single-surgeon, eyes undergoing phacoemulsification will be randomized to high (IOP 65mmHg) or low (IOP 25mmHg) IOP, contralateral eye will receive other treatment.

**Study treatment & Methods:**

- Sequential cataract surgery with similar cataract grade 2-3+ based on LOCS III grading bilaterally; 2nd eye to be completed within 2-3 weeks of first eye
- Randomize first eye to low vs high IOP, contralateral eye receives opposite IOP
- Patient education on VAS with standard script
- Standard pre-op drops: 2 drops of cyclopentolate 1%, tropicamide 1%, flurbiprofen sodium (Ocufen 0.03%), phenylephrine hydrochloride 2.5%, and 3 drops of marcaine 0.05%
- After draping, patients receive OcuCoat on cornea and 3 drops of lidocaine, 1mg of Versed (midazolam for anxiety with no analgesic effects)
- If patients experienced breakthrough pain during surgery, additional topical anesthetic, intracameral lidocaine, and/or opioid will be used per surgeon discretion and stage recorded
- Physiological responses recorded: Anesthesiologist will monitor patients per standard of care but will record additional BP/HR values at the start of the case (room entry), 4 minutes after versed is administered, during phacoemulsification, and during viscoelastic removal.
- Technique and Intraoperative recordings:
  - Single surgeon, uniform corneal incision construction (size, architecture) and use of Intrepid coaxial polymer I/A curved, Alcon OVD-Duovisc; Horizontal phaco-chop technique with preestablished, standardized, and optimized fluidic parameters
  - VAS score is asked at beginning of: phaco, cortex infusion /aspiration, viscoelastic removal
  - Surgeon assessment on patient cooperation and overall experience
  - Recording of intraoperative phacoemulsification metrics to ensure comparable parameters to eliminate variables other than IOP that may contribute to physiological changes
  - CDE, ASM activation, total aspiration time

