**Key Assessments:**

Percent of patients in each group requiring treatment for breakthrough discomfort/pain

Discomfort/pain score at phaco, I/A, visco removal (Real time VAS scoring)

- VAS score : 0 – no pain, 10 – unbearable pain
- VAS scored after each stage with false positive and false negative controls that are utilized to disqualify subjects out of study
- False positive: visco injection/capsulorhexis - should not experience pain
- False negative: drape removal – should experience pain/pressure (alert enough to participate)

Physiologic Responses associated with pain/inflammation: Blood pressure, Pulse rate

Surgeon Experience: Assessment on patient cooperation & surgeon intraoperative experience. Surgeon assessment on patient cooperation: poor, good, excellent:

- 1- Poor cooperation: could not follow instructions, lid squeezing, patient had frequent eye & head movements
- 2- Good cooperation: able to follow directions 50% of the time, some lid squeezing and patient movement
- 3- Excellent cooperation: able to follow directions >80% of the time with limited lid squeezing and patient movement

Surgeon assessment on overall experience: poor, good, excellent

- 1- Poor: fluctuating chamber (reverse pupillary block or surge) and reduced efficiency (nucleus & cortex removal)
- 2- Good: >75% chamber stability and adequate efficiency
- 3- Excellent: Minimal to no fluctuating chamber and excellent efficiency

Cost-analysis on intraoperative pharmacological agents utilized between high vs low IOP

Sub-analysis on subjects with axial length >24.5mm

Time Interval between Surgery Completion and Discharge from Facility to evaluate post-op efficiency and recovery time of patients

- Follow up- Patient Surveys:
  - Post op day 1 patient survey on experience (Iowa Satisfaction with Anesthesia Scale (ISAS))
  - Post op day 1 survey on patient preference - What eye was more comfortable? (R/L) What surgical experience did you enjoy more? (R/L)
  - x% of eyes would undergo the same procedure again
  - x% of eyes would recommend the procedure to family and friends

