#### **Planned Data Analysis:**

The following analysis will be performed using STATA software (v16.1, College Station, TX). All continuous variables will be summarized using mean, standard deviation and standard error. All binary measures will be summarized as proportions with standard deviation. The results of the test for normality on each continuous measure (the Shapiro-Wilk test) will determine whether the paired t-test or the Wilcoxon Sign Rank test will be used. McNemar's test will be used to compare proportions in binary outcome data, and the chi-squared test will be used to analyze the categorical outcome.

The analysis will follow a hierarchical approach using the following order of testing, only proceeding to the next test if the prior test achieves statistical significance at a level of 0.05.

Primary endpoint: comparing low vs. high IOP groups

1. Proportion of patients requiring rescue medication for breakthrough pain

Secondary Endpoints: comparing low vs. high IOP groups

1. Discomfort/pain score (VAS) - CONTINUOUS
  - a. Phacoemulsification
  - b. I/A
  - c. Visco removal

2. Surgeon Experience - CONTINUOUS
  - a. Patient cooperation
  - b. Surgeon experience
3. Cost analysis of intraoperative medications used - CONTINUOUS
4. Discomfort/pain score (VAS) on subjects with axial length of >24.5mm - CONTINUOUS
  - a. Phacoemulsification
  - b. I/A
  - c. Visco removal
5. Post op day 1 patient survey on experience (Iowa Satisfaction with Anesthesia Scale (ISAS) - CONTINUOUS
6. Proportion of patients following each procedure who would undergo the same procedure again - BINARY
7. Proportion of patients following each procedure who would recommend the procedure to family and friends - BINARY
8. Time Interval between Surgery Completion and Discharge from Facility - CONTINUOUS
9. Post op day 1 survey on patient preference - Which eye was more comfortable? (R/L/Neither) - CATEGORICAL
10. Which surgical experience did you enjoy more? (R/L/Neither) – CATEGORICAL
11. Proportion of patients who experience a significant (as defined by Crandall) physiologic response by a masked anesthesiologist - BINARY
  - a. Change in diastolic BP from baseline
  - b. Change in systolic BP from baseline
  - c. Change in pulse rate from baseline

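### Recording phaco metrics cannot isolate IOP, because each IOP setting is tied to one console; only the console-plus-setting contrast is estimable, and the protocol should say so

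*Protocol*

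**What the plan says.** Four places in the Protocol bear on this.

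- **Objective/ Unmet Medical Need** (and the Study Objective on the first page) sets the comparison as "Unity VCS/CS with Intelligent Fluidics at a low IOP setting and Centurion with Active Sentry at a traditionally high IOP setting". The Study Design table lists Unity as the product and Centurion as the comparator.
- **Design** has two conditions, 25 mmHg and 65 mmHg. One eye is randomised to one of them and the fellow eye gets the other.
- **Study treatment & Methods** gives the reason for collecting phaco data: "Recording of intraoperative phacoemulsification metrics to ensure comparable parameters to eliminate variables other than IOP that may contribute to physiological changes". The metrics named are CDE, ASM activation and total aspiration time.
- **Introduction**, first sentence, describes the study as "investigating the impact of high vs low IOP on the intraoperative experience and comfort for the patient and surgeon", with no console named.

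The Methods clause speaks of physiological changes. Key Assessments shows what that covers: "Physiologic Responses associated with pain/inflammation: Blood pressure, Pulse rate". These outcomes form the last item of the testing order in Planned Data Analysis, beginning with "Change in diastolic BP from baseline".

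**The concern.** The Methods clause separates IOP from everything else and says the recording serves to remove the rest. A reader, or the author of the study report, could take it that any difference in blood pressure or pulse is due to pressure as such. The first sentence of the Introduction invites the same step for patient comfort and surgeon experience. But two things change together between a patient's eyes: the pressure setting and the machine.

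The protocol does not treat the machine as neutral. Its statement of need says: "The advanced fluidics of Unity VCS/CS allow a more physiologic cataract surgery environment". The surgeon's rating of overall experience reserves its lowest grade for "fluctuating chamber (reverse pupillary block or surge) and reduced efficiency", features that a console could plausibly affect at any setting. At stake is which cause a positive result may be credited to. Whether the comparison itself is valid is not in question.

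**Working it through.** **Inputs.** 85 subjects and 170 eyes (Study Design table; 85 × 2 = 170). One eye per condition (Design). Low setting with Unity and high setting with Centurion (Objective). No other figure in the plan enters the argument.

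**Step 1: fill the four possible cells.**

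| | Low IOP | High IOP |
|---|---|---|
| Unity | 85 eyes | 0 eyes |
| Centurion | 0 eyes | 85 eyes |

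Pairs in which IOP differs and the console is the same: 0 of 85. Pairs in which the console differs and IOP is the same: 0 of 85.

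**Step 2: what can be estimated.** Let L = 1 for a low-IOP eye and 0 otherwise, and U = 1 for a Unity eye and 0 otherwise. Write the mean outcome as a + b·L + c·U. By Step 1, L = U in every eye, so the columns for L and U are identical and the three-column model has rank 2. The expected within-patient difference is (a + b + c) − a = b + c. Only this sum can be estimated. Any split of it between b (IOP) and c (console) fits the data equally well. This is as true at 58 or 67 pairs (Sample Size Justification) as at 85.

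**Step 3: whether the recorded metrics help.** Add the metrics M to the model: a + b·L + c·U + g·M. L and U are still identical, so b and c remain inseparable. The metrics are also recorded after assignment, and console or setting may influence them. They can show whether the two procedures looked alike on those three measures, but they cannot remove the console difference.

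**Step 4: reach of the two statements.** Counted in the order of Planned Data Analysis, the primary endpoint is 1 test. Secondary items 1 to 10 hold 3 + 2 + 1 + 3 + 1 + 1 + 1 + 1 + 1 + 1 = 15 tests. The three blood pressure and pulse comparisons are therefore tests 17, 18 and 19 of 19, and the Methods clause, read literally, concerns only these. The Introduction's wording on comfort and surgeon experience is broader. The aliasing in Step 2 applies to every endpoint.

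**The case against.** The strongest reply is that the governing text is already right. The objective, the comparator and the clinical message all name both consoles with their settings. The Introduction's first sentence uses the same low/high shorthand found throughout, and its next sentence names both machines. The Methods clause states a purpose, its natural object is the phaco parameters, and no planned test depends on it. Technique, incision and fluidic parameters are also standardised.

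Most of this stands. It is why the point concerns wording and attribution, and why the Introduction is the lesser part of it. The labels in Planned Data Analysis are acceptable shorthand once the groups are defined. The reply does not rescue the Methods clause: a text that speaks of removing variables other than IOP is no longer using IOP as a label for the package. Standardising technique reduces other sources of variation but leaves two different machines.

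A reader might infer more: that the low-versus-high comparison is invalid, that the primary analysis must change, or that a console effect has been shown. The documents support none of these. The package contrast is randomised and estimable, and nothing in the protocol gives the size of a console effect. Dividing the planned 15% versus 0% difference between IOP and console would need assumptions that the protocol does not supply.

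**Conclusion.** The point holds as a correction of wording with a real consequence for what may be concluded. The Methods clause ascribes to the design a property it does not have. The trial can estimate Unity at the low setting versus Centurion at the high setting and cannot assign any part of a difference to IOP alone. The size is structural: 0 of 85 pairs vary IOP with the console held fixed. This rests on one reading, that the pairing in the objective applies to every eye; the protocol describes no other combination. The Introduction's first sentence should be brought into line, but it is loose phrasing of an objective correctly stated elsewhere.

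**What to change.** Three edits to the Protocol:

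1. **Study treatment & Methods.** Replace the clause about removing variables other than IOP with: *CDE, ASM activation and total aspiration time are recorded to describe procedural comparability between the groups.*
2. **Design.** Add one definition: *The low and high IOP groups denote Unity VCS/CS at the low setting and Centurion with Active Sentry at the high setting. Differences between them will not be attributed to IOP alone or to the console alone.*
3. **Introduction, first sentence.** Reword the aim so that it names the same console-plus-setting comparison as the objective.

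The objective, the clinical message and the group labels in the analysis section can stay. Endpoints, tests, testing order and the 85 subjects do not change. The cost is a narrower causal claim, with no statement about IOP as an isolated cause. Such a statement would need a different design, in which console and setting are not tied together.

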**Key Assessments:**

Percent of patients in each group requiring treatment for breakthrough discomfort/pain

Discomfort/pain score at phaco, I/A, visco removal (Real time VAS scoring)

- VAS score : 0 – no pain, 10 – unbearable pain
- VAS scored after each stage with false positive and false negative controls that are utilized to disqualify subjects out of study
- False positive: visco injection/capsulorhexis - should not experience pain
- False negative: drape removal – should experience pain/pressure (alert enough to participate)

Physiologic Responses associated with pain/inflammation: Blood pressure, Pulse rate

Surgeon Experience: Assessment on patient cooperation & surgeon intraoperative experience. Surgeon assessment on patient cooperation: poor, good, excellent:

- 1- Poor cooperation: could not follow instructions, lid squeezing, patient had frequent eye & head movements
- 2- Good cooperation: able to follow directions 50% of the time, some lid squeezing and patient movement
- 3- Excellent cooperation: able to follow directions >80% of the time with limited lid squeezing and patient movement

Surgeon assessment on overall experience: poor, good, excellent

- 1- Poor: fluctuating chamber (reverse pupillary block or surge) and reduced efficiency (nucleus & cortex removal)
- 2- Good: >75% chamber stability and adequate efficiency
- 3- Excellent: Minimal to no fluctuating chamber and excellent efficiency

Cost-analysis on intraoperative pharmacological agents utilized between high vs low IOP

Sub-analysis on subjects with axial length >24.5mm

Time Interval between Surgery Completion and Discharge from Facility to evaluate post-op efficiency and recovery time of patients

- Follow up- Patient Surveys:
  - Post op day 1 patient survey on experience (Iowa Satisfaction with Anesthesia Scale (ISAS))
  - Post op day 1 survey on patient preference - What eye was more comfortable? (R/L) What surgical experience did you enjoy more? (R/L)
  - x% of eyes would undergo the same procedure again
  - x% of eyes would recommend the procedure to family and friends

#### **Primary Endpoint:**

% of pts in each group requiring rescue medication for breakthrough discomfort/pain

#### **Secondary endpoints:**

- Discomfort/pain score at phaco, I/A, visco removal
- Surgeon Experience: Assessment on cooperation & experience
- Cost-analysis on intraoperative medications utilized in high vs low IOP groups
- Breakthrough pain and discomfort/pain score on subjects with axial length of >24.5mm
- Post op day 1 patient survey on experience (Iowa Satisfaction with Anesthesia Scale (ISAS))
- Post op day 1 survey on patient preference - What eye was more comfortable? (R/L)
- What surgical experience did you enjoy more? (R/L)
- x% of eyes would undergo the same procedure again
- x% of eyes would recommend the procedure to family and friends
- Physiologic responses by masked anesthesiologist: BP, pulse rate
- Time Interval between Surgery Completion and Discharge from Facility

#### **Study Procedures:**

Duration of study will be approximately 13 months. At the time of their initial evaluation, consent process will include regular discussion and informed consent for cataract surgery. Risks, benefits, and alternatives to cataract surgery will be discussed. Patients who meet inclusion criteria will be offered additional discussion regarding the study. This discussion will include the elective nature of the study and detailed discussion of the informed consent document provided by surgeon (with study coordinators readily available). In addition, a copy of the informed consent document will be provided to the patient for their review.

#### **Study Rationale:**

The study will involve MAC (Monitored Anesthesia Care) for all patients; this is used for all cataract surgeries in our center. This style of anesthesia includes baseline topical anesthetic drops (Marcaine) placed in pre-op, anesthesiologist administering baseline anxiolytic medication (Midazolam) in the operating room, and just prior to initiating surgery surgeon administers lidocaine. With all cases in our facility, both the surgeon and anesthesiologist monitor for comfort, cooperation, and need for

additional anxiolytic or analgesia. The goal of MAC anesthesia is to provide comfort. While we strive for a pleasant experience for our patients, this is not general anesthesia, and there is a desire for patients to have the ability to follow commands. While some patients have some element of amnesia with this form of anesthesia, not all do. Participation in the study will not prevent surgeon or anesthesia professionals from adding additional anesthesia throughout the case if required for comfort or cooperation.

